## 6.2.2. Description of recruitment plan

See Section 4.4.2

## 6.2.3. Informed consent process and plan

A common template for the informed consent form will be used at each clinical site with modifications in the format as necessary to meet the requirements of the respective institutional human subjects committees. The parents/guardians will retain a copy of the signed consent form; the original signed consent will be retained in the subject's medical record and a copy will be included in the research records. No collection of data related

to the study or to procedures will be done prior to completion of the informed consenting process.

# 6.2.4. Assent

Assent will not be sought from study subjects because they will be infants at entry and during the duration of this study.

## 6.3. Potential Benefits

## 6.3.1. Description of possible health benefits to subjects

The use of IVIG as an adjuvant therapy following HPE has the potential to reduce hepatic and bile duct inflammation and increase bile drainage in infants with biliary atresia following the HPE surgery. This is based on the beneficial anti-inflammatory effects of IVIG in a variety of other immune-mediated or autoimmune diseases in children and in adults. We anticipate that improved bile drainage 90, 180 days or 360 days after HPE will lead to better long-term outcome, however this study is not designed to test that hypothesis. The design of this clinical trial within CHILDREN will allow us to generate data on short term clinical outcomes that may inform the need for a larger randomized more prolonged clinical trial to define efficacy and safety of IVIG. Given the relatively low toxicity profile of IVIG in infants and children, we believe that the potential therapeutic benefit for future patients with biliary atresia justifies the use of this treatment in this phase 1/2A research study.

## 6.3.2. Description of any incentives or rewards offered for participation

Parents or guardians of infants enrolled in the study will receive a small stipend in compliance with local policies per outpatient visit to reimburse them for meals and/or parking fees according to costs at each clinical site. The supplies of IVIG will be provided to each study site. In addition, the clinical site research pharmacy will provide a supply of prescribed doses of ursodeoxycholic acid, and trimethoprin-sulfamethoxasole. The provision of these items at no cost to the family will help minimize variations in routine clinical care among CHILDREN clinical sites, and may serve as an incentive to study participation.

## 6.3.3. Tests performed as part of research

Laboratory tests to evaluate side effects of the IVIG (e.g., electrolytes, BUN and creatinine, serum total IgG), will be paid for by the research grant. Mechanistic research blood tests will also be paid for by the research grant.

## 6.4. Summary of importance of knowledge to be gained from this research

Knowledge gained from this phase I/IIa clinical trial may increase the generalizable knowledge about the mechanisms involved in the pathogenesis of biliary atresia and its potential response to IVIG as a therapeutic agent. The risks of this study represent a minor increase above minimum risk. Currently there is no direct evidence of a benefit of IVIG in biliary atresia (it has not been reported to have been used in this disease), however many other immune and autoimmune-mediated inflammatory diseases have

been shown to respond to IVIG, justifying the plausibility of IVIG as a therapy for biliary atresia. Mechanistic studies in this protocol may provide insight into immunologic processes involved in the pathogenesis of BA that may be altered by IVIG therapy. It should be emphasized that biliary atresia currently has very poor treatment options but has very serious clinical consequences. The results of this study may provide the justification for further testing of a readily available, safe therapy for treatment of biliary atresia, i.e., IVIG. The experimental design of this trial will provide important information about short term feasibility, tolerability and safety of IVIG administration in this population of young patients. The results of this study could also provide some initial evidence of potential benefit of IVIG in biliary atresia. This combined new knowledge gained from this study should be of value in determining if a larger phase 2 or 3 clinical trial of IVIG should be entertained in infants with BA.

# 7. DATA AND SAFETY MONITORING PLAN (DSMP)

#### 7.1. Summary of DSMP

The DSMP aims to monitor this research protocol with emphasis on patient safety and data integrity. To this end, implementation of the DSMP outlined below will: 1) monitor the progress of the trial and the safety of participants, 2) assure compliance with requirements regarding the reporting of adverse events, 3) assure that any action resulting in a temporary or permanent suspension of the trial is reported to the DCC, CHILDREN Steering Committee and NIDDK, and 4) assure data accuracy and protocol compliances. General monitoring guidelines have been developed by CHILDREN to aid implementation of the DSMP, which will systematically monitor for the following:

- Verification that patient consent for study has been properly obtained and documented ensuring compliance with standards for protection of human subjects
- Verification that research subjects entered into the study meet inclusion and exclusion criteria
- Verification that the study is conducted in compliance with the protocol
- Verification of accuracy of the data collected
- Verification that all essential documentation required for good clinical practice guidelines are present, current, and appropriately filed.
- Verification of subjects completing the study

Particular attention will be given to monitoring patient safety issues. To this end, a Study Medical Safety Officer, independent of all investigators in the study, will be assigned for this clinical trial, and notification forms have been developed to expedite and facilitate the reports of serious adverse events. The DSMP will be overseen by the NIDDK and the Data and Safety Monitoring Board (described below).

## 7.2. Adverse events (AE) and serious adverse event (SAE)

#### 7.2.1. Adverse events (AE) – Overview

IVIG has not been used in infants with BA following HPE to our knowledge. However, IVIG has been used to treat immune deficiencies, Kawasaki disease, neonatal hemochromatosis and idiopathic thrombocytopenic purpura (ITP) in infants and young children previously, and has been tested in small preterm infants as a therapy to reduce the risk for infection and sepsis. In this study, we will monitor for potential adverse effects appropriately at each scheduled visit. Patients will be followed until complete/adequate resolution of an adverse event is documented. We will continue the evaluation of adverse events if a subject withdraws or is prematurely discontinued from participation in the study for any reason. The list of potential expected adverse effects was developed based on information from the package insert of IVIG and reviews of the published clinical trials of IVIG in the diseases mentioned above (45-46). Notably, some of the potential adverse effects of IVIG may also be present in infants with BA due to the natural progression of disease to biliary cirrhosis, such as fever, rashes, and impaired response to routine immunizations. Therefore, it is important in this study that the frequency, severity and seriousness of adverse effects, as well as their likely causality, be assessed in subjects receiving study medication.

#### 7.2.2. Grading of AEs

An AE is any unfavorable or unintentional sign (including abnormal laboratory findings), symptom, or disease temporally associated with the use of a medicinal product, whether or not considered related to the medicinal product. Grading of AEs will be based on the National Cancer Institute-Common Terminology Criteria for Adverse Events. Severity of AEs is outlined below:

- Grade 1: Mild adverse event
- Grade 2: Moderate adverse event
- Grade 3: Severe adverse event
- Grade 4: Life-threatening or disabling adverse event
- Grade 5: Death related to adverse event

#### 7.2.3. Serious Adverse Events (SAE) or Serious Suspected Adverse Reaction

#### Serious Adverse Event or Serious Suspected Adverse Reaction

An adverse event or suspected adverse reaction is considered "serious" if, in the view of either the investigator or sponsor, it results in any of the following outcomes:

- Death,
- A life-threatening adverse event
- Inpatient hospitalization or prolongation of existing hospitalization
- A persistent or significant incapacity or substantial disruption of the ability to conduct normal life functions
- A congenital anomaly/birth defect.

Important medical events that may not result in death, be life-threatening, or require hospitalization may be considered serious when, based upon appropriate medical judgment, they may jeopardize the patient or subject and may require medical or surgical intervention to prevent one of the outcomes listed in this definition. Examples of such medical events include allergic bronchospasm requiring intensive treatment in an emergency room or at home, blood dyscrasias or convulsions that do not result in inpatient hospitalization, or the development of drug dependency or drug abuse. The term SAE is not intended as a measure of severity or intensity.

#### Suspected Adverse Reaction

A Suspected Adverse Reaction is any adverse event for which there is a reasonable possibility that the drug caused the adverse event. For the purposes of IND safety reporting, "reasonable possibility" means there is evidence to suggest a causal relationship between the drug and the adverse event. Suspected adverse reaction implies a lesser degree of certainty about causality than adverse reaction, which means any adverse event caused by a drug.

#### Unexpected Adverse Event or Unexpected Suspected Adverse Reaction

An adverse event or suspected adverse reaction is considered "unexpected" if it is not listed in the investigator brochure or is not listed at the specificity or severity that has been observed; or, if an investigator brochure is not required or available, is not consistent with the risk information described in the general investigational plan or elsewhere in the current application, as amended. For example, under this definition, hepatic necrosis would be unexpected (by virtue of greater severity) if the investigator brochure referred only to elevated hepatic enzymes or hepatitis. Similarly, cerebral thromboembolism and cerebral vasculitis would be unexpected (by virtue of greater specificity) if the investigator brochure listed only cerebral vascular accidents. "Unexpected", as used in this definition, also refers to adverse events or suspected adverse reactions that are mentioned in the investigator brochure as occurring with a class of drugs or as anticipated from the pharmacological properties of the drug, but are not specifically mentioned as occurring with the particular drug under investigation.

## Expected Adverse Event or Expected Adverse Reaction

Expected events are any adverse experiences that have been identified in nature or severity in the current investigator brochure and/or protocol.

## 7.3. AE and SAE reporting plan

An independent physician not involved in the study will serve as the Medical Safety Officer, reviewing all SAEs promptly after being reported in the database by the clinical sites. The Medical Safety Officer will prepare a final SAE narrative report for each SAE which will be distributed to the NIDDK Program Director and DSMB Chair. In addition, the DSMB will review all AEs during their regularly scheduled meetings, or on an expedited basis as determined by the NIDDK Program Director, who will solicit the input of the Chair of the DSMB as needed

All adverse events are reported to the DCC by completion of the Adverse Events Form. All SAEs as defined previously require expedited event notification within 24 hours of occurrence or identification to the DCC.

Once the SAE is resolved, a final report is generated by the Medical Safety Officer. The final report will be sent to the clinical site PI to review for accuracy and completeness of the report. Following review by the clinical site PI, the Medical Safety Officer will send the final report to the NIDDK Program Director, clinical site PI, and the DCC PI and Project Manager. All SAE reports will go to the DSMB for review during their regularly scheduled meetings. The FDA definitions and requirements for expedited reporting will be used to determine if any individual SAE warrants notification to the FDA and to the IRBs of all participating CHILDREN clinical sites.

The clinical site at which the SAE occurred is responsible for expedited reporting of the SAE to their respective IRB. Each site is responsible to report all AE's to their IRB according to its AE reporting policy and procedures.

On behalf of the NIDDK, the Data Coordinating Center will submit an expedited safety report to the FDA for all serious unexpected suspected adverse reactions (SUSARs). That is, when the SAE is unexpected and may be related to the study drug based on evidence of causality. This report will include information on frequency of similar events along with a narrative of similar events to provide context for the individual report. Copies of the expedited safety report will be provided to NIDDK, DSMB, and site investigators.

## 7.4. Monitoring and management for specific AEs

Several side effects of IVIG may occur in the subjects during this trial. The following section outlines the plan for monitoring and management of these AEs. This monitoring will be conducted after HPE but before the first dose of study medication is given (to provide baseline data) and then at hospital discharge and at each scheduled follow up visit.

## 7.4.1. Elevation in Blood Pressure related to Increased Fluid Volume

Although unlikely, hypertension could develop due to the fluid volume administered with each IVIG infusion in this study (20 ml per kg body weight over 6-8 hours for each infusion). Vital signs will be continually monitored during the IVIG infusions per institutional protocol. If hypertension develops (systolic BP ≥112 mmHg) during an IVIG infusion, the infusion rate will be reduced or stopped and BP will be measured again in 30 minutes. If BP remains elevated, intravenous furosemide (1 mg/kg/dose) will be an option based on the clinical judgment of the treating physician if fluid volume is considered the likely cause of the hypertension. Alternatively, if the patient is asymptomatic, BP can be re-measured for 30 minutes without treatment. Blood pressure will continue to be monitored each 15 minutes until resolution of the hypertension. If the IVIG infusion must be stopped completely, the subject will not receive further doses of IVIG.

Additional treatment options for the hypertension include:

- a. Treatment choices for hypertension with BP ≥112 mmHg without symptoms
  - Hydrochlorothiazide: 2 mg/kg/day given once or twice a day, or
  - Amlodipine: 0.2-0.4 mg/kg/day given once or twice a day, or
  - Captopril: 0.3-1 mg/kg/day given twice a day
  - Other site-specific treatment choice
- b. Treatment choices for hypertension with BP ≥112 mmHg with symptoms
  - Nifedipine 0.25-0.5 mg/kg/ sublingual
  - Labetolol: 1-3 mg/kg/hour IV
  - Other site-specific treatment of choice

#### 7.4.2. Irritability

The development of severe irritability in the subject without an obvious cause will be considered a moderate AE, defined as the presence of inconsolable, persistent crying without an apparent cause, which requires evaluation and confirmation by the primary care provider or a visit to an emergency department if the patient is being followed as an outpatient, or evaluation by the clinical inpatient or outpatient team if the patient is in hospital receiving IVIG infusion at the time of the event. If the severe irritability develops during an IVIG infusion, the infusion will be slowed down or stopped. Following evaluation for irritability and if no obvious cause is identified, the subject will be treated symptomatically and will not receive additional doses of IVIG. Consideration for a lumbar puncture and evaluation for the rare aseptic meningitis syndrome (see 7.4.4) that has been reported with IVIG therapy will be based on the clinical discretion of the treating physician. The irritability may also be a manifestation of headaches that occur in 20-30% of adults who receive comparable doses of IVIG.

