#### 4.3.1. **Primary Outcome Measures**:

- 1. Feasibility: Percentage of subjects for whom administration of IVIG is feasible, defined as the successful administration (at least 80% of each dose) of the 3 doses of IVIG at the prescribed times through peripheral IV lines or central lines if already in place for clinical indications.
- 2. Acceptability: Percentage of subjects for whom the study is acceptable, defined as the ability of the subject's family or guardian to allow intravenous line placements, blood draws, and other study procedures for the study subjects.
- 3. Safety and tolerability measures:
  - a. Percentage of subjects with any serious adverse events (SAEs),
  - b. Percentage of subjects with any level 3, 4, or 5 toxicity (per NCI CTEP grading system [http://www.eortc.be/services/doc/ctc/ctcaev3.pdf], and
  - c. Percentage of subjects with other expected adverse events (such as allergic reactions, irritability, fluid volume problems, IV infiltration and aseptic meningitis).

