# Aim 1: To determine the feasibility, acceptability, tolerability and safety profile of IVIG treatment after HPE for biliary atresia.

**Hypothesis 1:** Administering IVIG will be feasible, acceptable and well tolerated in infants with BA without significant toxicity.

The percentage of subjects (and one-sided 90% Clopper-Pearson lower confidence bounds) in which the study is feasible and acceptable will be calculated. Point estimates and one-sided 90% Clopper-Pearson lower confidence bounds will be calculated for safety and tolerability parameters.

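### Section 7.4.2 presets severe unexplained irritability as a moderate event, against the protocol's own grade scale, which can keep isolated cases out of primary safety outcome 3b

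*Protocol*

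**What the plan says.** Section 7.4.2 covers irritability, one of the IVIG reactions the protocol expects. It says: "The development of severe irritability in the subject without an obvious cause will be considered a moderate AE". The event is "defined as the presence of inconsolable, persistent crying without an apparent cause", with the further condition that it needs clinical evaluation. If no cause is found, the infant gets no more IVIG.

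Section 7.2.2 sets the general rule: "Grading of AEs will be based on the National Cancer Institute-Common Terminology Criteria for Adverse Events". Its list reads "Grade 2: Moderate adverse event" and "Grade 3: Severe adverse event". Section 4.12.3, on stopping study medication, likewise equates a severe adverse event with level 3, 4 or 5.

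Section 4.3.1 makes three safety percentages primary outcomes:

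- 3a counts infants with any serious adverse event.
- 3b is the "Percentage of subjects with any level 3, 4, or 5 toxicity" on the NCI scale.
- 3c is the "Percentage of subjects with other expected adverse events". It names irritability and sets no grade threshold.

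For the analysis, Section 5.3 (Aim 1) says: "Point estimates and one-sided 90% Clopper-Pearson lower confidence bounds will be calculated for safety and tolerability parameters".

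**The concern.** On the protocol's own scale the word *severe* means Grade 3 and *moderate* means Grade 2. Section 7.4.2 takes an event it calls severe and fixes it at moderate before any infant has been assessed. It gives no reason and does not say that it overrides Section 7.2.2.

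Outcome 3b begins at Grade 3, so the preset label puts this reaction just below the threshold. Two sites could grade the same episode differently, one by Section 7.4.2 and the other by Section 7.2.2. Any error that comes from following Section 7.4.2 goes one way: it lowers 3b. The grade is assigned at the site, so an analysis that starts from recorded grades would not see the difference.

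**Working it through.** **Setting the sections side by side**

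| Section | Rule | Grade implied for severe unexplained irritability |
|---|---|---|
| 7.2.2 | NCI criteria; severe is Grade 3 | 3, if the protocol's word is taken at face value |
| 4.12.3 | Severe means level 3, 4 or 5 | 3 or higher |
| 7.4.2 | Considered moderate | 2 |
| 4.3.1, outcome 3b | Counts Grades 3 to 5 | Counted under the first two rows, not under the third |

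The definition in Section 7.4.2 has no upper limit. The worst episode that fits it gets the same label as the mildest.

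**Inputs**

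- Number treated, n: 23 to 29 (Section 5.2.1).
- Estimator: point estimate x/n with a one-sided 90% Clopper-Pearson lower bound (Section 5.3, Aim 1).
- Rate p of infants whose only Grade 3-level event is this one: not given. A range of 1% to 10% is assumed below.

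**The plan's own figures**

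Section 5.2.1 gives the chance of seeing at least one infant with a specific event. The formula is 1 − (1 − p)^n.

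| True rate | n = 23 | n = 29 | Protocol states |
|---|---|---|---|
| 20% | 99.4% | 99.9% | above 98% |
| 10% | 91.1% | 95.3% | 91 to 95% |
| 5% | 69.3% | 77.4% | 69 to 77% |

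These agree with the protocol.

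**Loss per infant left out of 3b**

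- n = 29: 1/29 = 3.4 percentage points.
- n = 23: 1/23 = 4.3 percentage points.

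**Effect on the planned bound**

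The lower bound for x infants out of n is the 10th percentile of a Beta(x, n − x + 1) distribution. As an illustration, suppose 5 infants should be counted and 4 are.

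| n | Counted | Point estimate | Lower bound |
|---|---|---|---|
| 29 | 5 | 17.2% | 8.6% |
| 29 | 4 | 13.8% | 6.2% |
| 23 | 5 | 21.7% | 11.0% |
| 23 | 4 | 17.4% | 7.8% |

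**How likely it is to arise at all**

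The same formula, with the assumed rates:

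| Assumed p | n = 23 | n = 29 |
|---|---|---|
| 1% | 21% | 25% |
| 5% | 69% | 77% |
| 10% | 91% | 95% |

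**The case against.** The best counter-reading is that the mapping is deliberate. On this view *severe irritability* names a symptom, Section 7.4.2 defines it operationally, and the grade is then assigned to that defined event. A specific rule would ordinarily override a general one, and a uniform rule for a subjective symptom could reduce variation between sites. The NCI wording for irritability is not in the protocol; if it would grade this event as 2, outcome 3b loses nothing. In addition, 3c names irritability, hospitalised cases enter 3a, the stopping criteria in Section 7.5 consider adverse events of any grade, and no decision threshold is tied to 3b.

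Much of this stands, and it limits the size of the problem. No case vanishes from primary safety reporting, and dosing does not depend on the grade. It cannot be said that every such episode is Grade 3.

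The objection does not remove the contradiction. A deliberate mapping would still depart, unexplained, from the scale in Section 7.2.2, and it leaves no route by which a worse episode could be Grade 3. Section 4.4.5 speaks separately of moderate irritability, so a lower term was available. If every site did follow Section 7.4.2, grading would be uniform, but any episode that truly reaches Grade 3 would be missing from 3b everywhere. Because 3c has no severity threshold, it cannot supply the missing count.

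**Conclusion.** The concern holds, at minor severity. Section 7.4.2 sets the grade of a named, expected reaction in advance, below the protocol's own word for it and below the threshold of a primary safety outcome.

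The consequence for 3b is conditional on three things: sites follow Section 7.4.2, the episode would otherwise be Grade 3 or higher, and the infant has no other event at that level. Where all three hold, the error is always downward, in both the estimate and its lower bound. How many infants would be affected is unknown, because the protocol gives no rate; the 1% to 10% range and the 5-versus-4 comparison are illustrations only.

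**What to change.** In Section 7.4.2, delete the preset moderate grade, or state that it is a minimum and not a cap. Grade irritability by the scale in Section 7.2.2, count any episode of Grade 3 or higher in 3b, and continue to list all irritability in 3c. Keep the rule that an infant with unexplained severe irritability gets no further IVIG.

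If the moderate label is intended, the alternative is to rename the event moderate irritability and define separately what would be Grade 3.

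The cost is a few words in one sentence. No data collection is added and dosing is unchanged. The reported Grade 3 to 5 percentage may rise slightly.
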